5.2.2 Timing of Dose Administration

Trial treatment should be administered on Day 1 of each cycle after all procedures/assessments have been completed as detailed on the Trial Flow Chart (Section 6.0). Trial treatment may be administered up to 3 days before or after the scheduled Day 1 of each cycle due to administrative reasons. Interruptions from the treatment plan for greater than 3 days and up to 3 weeks may be allowed, but require consultation between the investigator and Sponsor, and written documentation of the collaborative decision on subject management.

All trial treatments will be administered on an outpatient basis.

Pembrolizumab will be administered as a 30 minute IV infusion every 3 weeks. Sites should make every effort to target infusion timing to be as close to 30 minutes as possible. However, given the variability of infusion pumps from site to site, a window of -5 minutes and +10 minutes is permitted (ie, infusion time is 30 minutes: -5 min/+10 min).

The Pharmacy Manual contains specific instructions for pembrolizumab reconstitution, preparation of the infusion fluid, and administration.

5.2.3 Extent of Trial Treatment

- All subjects who experience a partial response or have stable disease may remain on treatment for up to 35 cycles (approximately two years) or until progression. Per the investigator's discretion subjects who achieve a CR are eligible to restart treatment upon documented progression as long as they meet eligibility criteria specified in the protocol (See Section 7.1.5.2.2).
- Subjects who achieve a CR and choose not to stop therapy may continue treatment for a total duration of 35 cycles (approximately two years).

5.2.4 Trial Blinding/Masking

This is an open-label trial; therefore, the Sponsor, investigator and subject will know the treatment administered.

5.3 Randomization or Treatment Allocation

Subjects participating in this trial will be allocated by non-random assignment.

5.4 Stratification

No stratification based on age, sex or other characteristics will be used in this trial.

5.5 Concomitant Medications/Vaccinations (Allowed & Prohibited)

Medications or vaccinations specifically prohibited in the exclusion criteria are not allowed during the ongoing trial. If there is a clinical indication for any medication or vaccination specifically prohibited during the trial, discontinuation from trial therapy or vaccination may be required. The investigator should discuss any questions regarding this with the Sponsor Clinical Director. The final decision on any supportive therapy or vaccination rests with the investigator and/or the subject's primary physician. However, the decision to continue the subject on trial therapy or vaccination schedule requires the mutual agreement of the investigator, the Sponsor and the subject.

5.5.1 Acceptable Concomitant Medications

All treatments that the investigator considers necessary for a subject's welfare may be administered at the discretion of the investigator in keeping with the community standards of medical care. All concomitant medication will be recorded on the case report form (CRF) including all prescription, over-the-counter (OTC), herbal supplements, and IV medications and fluids. If changes occur during the trial period, documentation of drug dosage, frequency, route, and date may also be included on the CRF. Subject may remain on anti-coagulation therapy as long as the PT or PTT is within therapeutic range of the intended use of anticoagulants

All concomitant medications received within 28 days before the first dose of trial treatment and 30 days after the last dose of trial treatment should be recorded. Concomitant medications administered 30 days after the last dose of trial treatment should be recorded for SAEs and ECIs as defined in Section 7.2.

5.5.2 Prohibited Concomitant Medications

Subjects are prohibited from receiving the following therapies during the Screening and Treatment Phase (including retreatment for post-complete response relapse) of this trial:

- Antineoplastic systemic chemotherapy or biological therapy
- Immunotherapy not specified in this protocol
- Chemotherapy not specified in this protocol
- Investigational agents other than pembrolizumab
- Radiation therapy
 - Any need for radiotherapy should be considered progressive disease and result in discontinuation of study therapy.
- Live vaccines within 30 days prior to the first dose of trial treatment and while participating in the trial. Examples of live vaccines include, but are not limited to, the following: measles, mumps, rubella, chicken pox, yellow fever, rabies, BCG, and oral typhoid vaccine. Seasonal influenza vaccines for injection are generally killed virus

vaccines and are allowed; however intranasal influenza vaccines (eg, Flu-Mist[®]) are live attenuated vaccines, and are not allowed.

- Systemic glucocorticoids for any purpose other than to modulate symptoms from an event of clinical interest of suspected immunologic etiology. The use of physiologic doses of corticosteroids may be approved after consultation with the Sponsor.

Subjects who, in the assessment by the investigator and after consultation with the Sponsor, require the use of any of the aforementioned treatments for clinical management should be removed from the trial. Subjects may receive other medications that the investigator deems to be medically necessary.

The Exclusion Criteria describes other medications which are prohibited in this trial.

There are no prohibited therapies during the Post-Treatment Follow-up Phase. Subjects must be discontinued from the active follow-up phase if they begin a non-trial treatment for their underlying disease.

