After the end of treatment, each subject will be followed for 30 days for adverse event monitoring (serious adverse events and events of clinical interest [ECIs] will be collected for 90 days after the end of treatment). Subjects who discontinue treatment for reasons other than disease progression will have post-treatment follow-up for disease status until disease progression, initiating a non-study cancer treatment, withdrawing consent, or becoming lost to follow-up. All subjects will be followed for overall survival until death, withdrawal of consent or the end of the study, whichever comes first.

The primary objectives of the trial are to determine safety, tolerability, and overall response rate (ORR) by independent central review (utilizing the IWG response assessment criteria per Cheson 2007) of pembrolizumab in subjects with relapsed and/or refractory classical Hodgkin Lymphoma. Secondary objectives include further analysis of various efficacy parameters (complete remission rate [CRR], progression free survival [PFS], overall survival [OS] and duration of response [DOR]). Response assessments, by independent central

review, utilizing the 5-point scale according to the Lugano Classification; analysis of PD-L1 expression and corresponding efficacy; changes in health related quality of life assessments, along with the relationship of candidate efficacy/resistance biomarkers and anti-tumor activity of pembrolizumab will be investigated as exploratory objectives.

Unless specified otherwise, the statistical analyses will be conducted separately by cohort. In addition, a separate clinical study report may be issued for a single cohort if the actual enrollment rate among cohorts is markedly different.

This trial will be conducted in conformance with Good Clinical Practices.

Specific procedures to be performed during the trial, as well as their prescribed times and associated visit windows, are outlined in the Trial Flow Chart - Section 6.0. Details of each procedure are provided in Section 7.0 – Trial Procedures.

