5.8 Subject Withdrawal/Discontinuation Criteria

Subjects may withdraw consent at any time for any reason or be dropped from the trial at the discretion of the investigator should any untoward effect occur. In addition, a subject may be withdrawn by the investigator or the Sponsor if enrollment into the trial is inappropriate, the trial plan is violated, or for administrative and/or other safety reasons. Specific details regarding discontinuation or withdrawal procedures; including specific details regarding withdrawal from Future Biomedical Research, are provided in Section 7.1.4 – Other Procedures.

A subject must be discontinued from the trial for any of the following reasons:

- The subject or legal representative (such as a parent or legal guardian) withdraws consent.

A subject must be discontinued from treatment (but may continue to be monitored in the trial) for any of the following reasons:

- The subject or legal representative (such as a parent or legal guardian) withdraws consent for treatment
- Documented disease progression Note: Subjects may continue to receive trial treatment beyond progression if the subject meets the criteria outlined in Section 7.1.2.6.7.
- Unacceptable adverse experiences as described in Section 5.2.1.2, 5.6.1, and 7.2
- Intercurrent illness that prevents further administration of treatment
- Investigator's decision to withdraw the subject
- The subject has a confirmed positive serum pregnancy test
- Noncompliance with trial treatment or procedure requirements
- The subject is lost to follow-up
- Administrative reasons

The End of Treatment and Follow-up visit procedures are listed in Section 6 (Flow Chart) and Section 7.1.5 (Visit Requirements). After the end of treatment, each subject will be followed for 30 days for adverse event monitoring (serious adverse events will be collected for 90 days after the end of treatment as described in Section 7.2.3.1). Subjects who discontinue for reasons other than progressive disease will have post-treatment follow-up for disease status until disease progression, initiating a non-study cancer treatment, withdrawing consent or becoming lost to follow-up. After documented disease progression or the start of new antineoplastic therapy each subject will be followed for overall survival until death, withdrawal of consent, or the end of the study, whichever occurs first.

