7.1.1.6.3 Subsequent Antineoplastic Therapy Status

The investigator or qualified designee will collect transplant parameters (ie. date and type of transplant, conditioning regimen), and will review all new antineoplastic therapy initiated after the last dose of trial treatment. If a subject initiates a new antineoplastic therapy within 30 days after the last dose of trial treatment, the 30 day Safety Follow-up visit must occur before the first dose of the new therapy. Once new antineoplastic therapy has been initiated the subject will move into survival follow-up.

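### Section 5.5.2 removes subjects who need a prohibited therapy from the trial, contradicting the survival follow-up rules elsewhere; where followed literally it censors OS early and probably informatively

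*Combined protocol and SAP*

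**What the plan says.** Section 5.5.2 lists therapies prohibited during the Screening and Treatment Phase, retreatment included. Among them are "Antineoplastic systemic chemotherapy or biological therapy", other immunotherapy, radiotherapy, live vaccines, and systemic glucocorticoids outside stated exemptions. Subjects who, in the investigator's assessment and after consulting the sponsor, "require the use of any of the aforementioned treatments for clinical management should be removed from the trial".

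The same section gives radiotherapy a different consequence: "Any need for radiotherapy should be considered progressive disease and result in discontinuation of study therapy". Its parent, section 5.5, says of prohibited medication only that "discontinuation from trial therapy or vaccination may be required".

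On follow-up, section 2.1 states: "All subjects will be followed for overall survival until death, withdrawal of consent or the end of the study, whichever comes first". Section 5.8 has two separate lists. The first opens "A subject must be discontinued from the trial for any of the following reasons" and has one entry, withdrawal of consent. The second opens "A subject must be discontinued from treatment (but may continue to be monitored in the trial) for any of the following reasons". Section 7.1.1.6.3 adds: "Once new antineoplastic therapy has been initiated the subject will move into survival follow-up". Section 7.1.5.4.2 and footnote c of the 6.1 flow chart say the same and set contacts about every 12 weeks.

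Overall survival (OS) is a secondary endpoint (8.4.1). Table 13 assigns it a Kaplan-Meier summary with censoring at the last assessment.

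**The concern.** Section 5.8 makes leaving the trial and leaving treatment different things, so the choice of term in 5.5.2 has consequences. Section 7.1.4.1 has final-visit activities done when a subject discontinues from the trial. A site that reads 5.5.2 as written could therefore close out a subject whom five other places in the protocol send into survival follow-up.

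For a subject who needs new lymphoma therapy while on pembrolizumab, that close-out would fall when prognosis has probably worsened. Kaplan-Meier then treats the subject as having the same later risk as those still under observation. Deaths after removal go uncounted and the OS curve reads too high. The trial has no control arm, so no internal comparison would offset the error.

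**Working it through.** No figure in the plan depends on this sentence, so there is nothing to reproduce. The check is a comparison of texts, followed by an illustration of size.

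**Step 1: what each place requires of a subject who needs new anticancer therapy while on treatment**

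| Place | Consequence |
|---|---|
| 5.5.2, general sentence | Leaves the trial |
| 5.5.2, radiotherapy bullet | Stops study therapy, counted as progression |
| 5.5 | May have to stop trial therapy |
| 2.1 | OS follow-up for all until death, consent withdrawal or study end |
| 5.8 | OS follow-up after progression or new antineoplastic therapy |
| 7.1.1.6.3, 7.1.5.4.2, footnote c of 6.1 | Moves into survival follow-up |

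Only the first row ends follow-up. Radiotherapy carries two different consequences within 5.5.2 itself.

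**Step 2: effect on OS if the first row is followed.** The subject stays in the ASaT (All Subjects as Treated) population, is censored at the last assessment under Table 13, and any later death is missed.

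**Step 3: effect on PFS and DOR.** Imaging already stops at new anticancer treatment (7.1.2.6.6). Table 12 censors PFS at the last assessment before it in the primary analysis, and 8.6.1.4 censors DOR in the same way. Removal for new anticancer therapy therefore adds nothing here. Added loss is confined to subjects removed for non-anticancer items, such as non-exempt systemic steroids or live vaccines.

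**Step 4: illustration of size.** Assumptions not taken from the documents: exponential time to progression with median 11 months, exponential survival after progression with median 24 months, no deaths before progression, and a fraction q of progressing subjects removed at progression.

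- λ = ln 2 / 11 = 0.0630 per month; μ = ln 2 / 24 = 0.0289 per month.
- Progression-free at t: A(t) = exp(−λt). Alive after progression: B(t) = λ[exp(−μt) − exp(−λt)] / (λ − μ).
- With full follow-up, OS at 24 months = A + B = 0.2204 + 0.5162 = 0.7366.
- With removal, the Kaplan-Meier hazard is h(t) = μ(1 − q)B / [A + (1 − q)B], and the estimate tends to exp(−∫h) over 0 to 24 months.

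| q | ∫h | OS estimate at 24 months | Overstatement (points) |
|---|---|---|---|
| 0 | 0.3057 | 73.7% | 0 |
| 10% | 0.2905 | 74.8% | 1.1 |
| 20% | 0.2737 | 76.1% | 2.4 |
| 40% | 0.2337 | 79.2% | 5.5 |

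The q = 0 row returns the full-follow-up value, as it should.

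**Sensitivity.** Replace the 24-month median by 1.2 years (14.4 months). Section 4.2.1.1 gives that figure for patients who relapse or progress within a year of auto-SCT, a related but different group. OS with full follow-up is then 62.1%, and the three estimates are 63.7%, 65.5% and 70.0%: overstatements of 1.6, 3.4 and 7.9 points. The direction is the same and the size depends on the inputs.

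**Scale.** For one cohort of 60, ignoring censoring, the 95% half-width at 73.7% is 1.96 × √(0.737 × 0.263 / 60) = 0.111, about 11 points.

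**The case against.** The best defence is that this is one loosely worded sentence against several consistent ones, and that few subjects would meet it. Much of that stands.

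- **Scope.** The list applies only in the Screening and Treatment Phase. Section 5.5.2 says that nothing is prohibited in post-treatment follow-up, and starting non-trial treatment there ends only active follow-up. A subject who progresses, stops pembrolizumab and then starts another therapy goes into survival follow-up by the ordinary route and never reaches the disputed sentence.
- **Prognosis.** Steroids for events of suspected immunologic cause are exempt, physiologic doses may be approved, and live vaccines say nothing about prognosis. Not everyone on the list is a poor-risk subject.
- **Discretion.** Section 5.8 also lets the investigator or sponsor withdraw subjects. Consent withdrawal is the only listed mandatory reason for leaving the trial, not the only possible one.
- **Safeguards.** Section 7.1.5.4.3 allows sponsor-requested survival sweeps of participants without a scheduled contact. Sections 7.2.3.1 and 7.2.3.2 keep the reporting windows for serious events, reporting of related serious events at any time, and 18 months of post-transplant events.

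A reader might infer that 5.5.2 ends survival follow-up for progressing subjects generally, drops poor-prognosis subjects from the OS analysis, and stops late safety and transplant data. The documents do not support that. Ordinary progressors have their own route, removed subjects remain in ASaT, and the reporting duties stand on their own.

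What the defence does not remove is the contradiction. Section 5.5.2 uses different terms for stopping therapy, leaving active follow-up and leaving the trial, so a site has reason to think the last was meant. The sweep does not clearly cover someone already removed.

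**Conclusion.** The contradiction is real and lies in current text. Where a site follows 5.5.2 literally, a subject who needs new lymphoma therapy while on treatment is censored early for OS. That censoring is probably informative, and the bias would be upward.

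The size is unknown because the documents do not say how many subjects would be removed. The illustration gives about 1 to 5.5 points at 24 months if 10% to 40% of progressing subjects were removed. Both medians and the removal fractions are assumptions, and because most progressors bypass the sentence, the upper fractions are hard to reach. At 10% to 20% the shift is small beside the roughly 11-point sampling half-width of one cohort.

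OS is secondary and not formally tested (8.3). The ORR test, its alpha and its power do not depend on this sentence. The point is worth correcting because the bias has a known probable direction and the correction costs almost nothing.

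**What to change.** Reconcile 5.5.2 with 5.5, 5.8 and 7.1.5.4. The sentence should state that subjects who need a listed therapy remain in the trial for disease-status or survival follow-up, as applicable, unless they withdraw consent. No change is proposed to which therapies are prohibited or to who receives or stops treatment.

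The cost is one sentence in an amendment and a note to sites. The 12-weekly contacts are already planned, and yearly efficacy updates already run until the trial is complete (text after Table 13). If any subject has already been closed out under 5.5.2, report the number by cohort with the OS results and seek vital status where consent allows.

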5.6 Rescue Medications & Supportive Care

5.6.1 Supportive Care Guidelines

Subjects should receive appropriate supportive care measures as deemed necessary by the treating investigator. Suggested supportive care measures for the management of adverse events with potential immunologic etiology are outlined below. Where appropriate, these guidelines include the use of oral or intravenous treatment with corticosteroids as well as additional anti-inflammatory agents if symptoms do not improve with administration of corticosteroids. Note that several courses of steroid tapering may be necessary as symptoms may worsen when the steroid dose is decreased. For each disorder, attempts should be made to rule out other causes such as metastatic disease or bacterial or viral infection, which might require additional supportive care. The treatment guidelines are intended to be applied when the investigator determines the events to be related to pembrolizumab.

Note: if after the evaluation the event is determined not to be related, the investigator is instructed to refer to Section 5.2.1.2 for dose modification guidelines.

It may be necessary to perform conditional procedures such as bronchoscopy, endoscopy, or skin photography as part of evaluation of the event.

- **Pneumonitis:**
 - For **Grade 2 events**, treat with systemic corticosteroids. When symptoms improve to Grade 1 or less, steroid taper should be started and continued over no less than 4 weeks.
 - For **Grade 3-4 events**, immediately treat with intravenous steroids. Administer additional anti-inflammatory measures, as needed.

- Add prophylactic antibiotics for opportunistic infections in the case of prolonged steroid administration.
- **Diarrhea/Colitis:**

Subjects should be carefully monitored for signs and symptoms of enterocolitis (such as diarrhea, abdominal pain, blood or mucus in stool, with or without fever) and of bowel perforation (such as peritoneal signs and ileus).

 - All subjects who experience diarrhea/colitis should be advised to drink liberal quantities of clear fluids. If sufficient oral fluid intake is not feasible, fluid and electrolytes should be substituted via IV infusion. For Grade 2 or higher diarrhea, consider GI consultation and endoscopy to confirm or rule out colitis.
 - For **Grade 2 diarrhea/colitis** that persists greater than 3 days, administer oral corticosteroids.
 - For **Grade 3 or 4 diarrhea/colitis** that persists > 1 week, treat with intravenous steroids followed by high dose oral steroids.
 - When symptoms improve to Grade 1 or less, steroid taper should be started and continued over no less than 4 weeks.
- **Type 1 diabetes mellitus (if new onset, including diabetic ketoacidosis [DKA]) or \geq Grade 3 Hyperglycemia, if associated with ketosis (ketonuria) or metabolic acidosis (DKA)**
 - For **T1DM** or **Grade 3-4 Hyperglycemia**
 - Insulin replacement therapy is recommended for Type I diabetes mellitus and for Grade 3-4 hyperglycemia associated with metabolic acidosis or ketonuria.
 - Evaluate patients with serum glucose and a metabolic panel, urine ketones, glycosylated hemoglobin, and C-peptide.
- **Hypophysitis:**
 - For **Grade 2** events, treat with corticosteroids. When symptoms improve to Grade 1 or less, steroid taper should be started and continued over no less than 4 weeks. Replacement of appropriate hormones may be required as the steroid dose is tapered.
 - For **Grade 3-4** events, treat with an initial dose of IV corticosteroids followed by oral corticosteroids. When symptoms improve to Grade 1 or less, steroid taper should be started and continued over no less than 4 weeks. Replacement of appropriate hormones may be required as the steroid dose is tapered.

- **Hyperthyroidism or Hypothyroidism:**

Thyroid disorders can occur at any time during treatment. Monitor patients for changes in thyroid function (at the start of treatment, periodically during treatment, and as indicated based on clinical evaluation) and for clinical signs and symptoms of thyroid disorders.

- **Grade 2** hyperthyroidism events (and **Grade 2-4** hypothyroidism):

- In hyperthyroidism, non-selective beta-blockers (eg, propranolol) are suggested as initial therapy.
- In hypothyroidism, thyroid hormone replacement therapy, with levothyroxine or liothyronine, is indicated per standard of care.

- **Grade 3-4** hyperthyroidism

- Treat with an initial dose of IV corticosteroid followed by oral corticosteroids. When symptoms improve to Grade 1 or less, steroid taper should be started and continued over no less than 4 weeks. Replacement of appropriate hormones may be required as the steroid dose is tapered.

- **Hepatic:**

- For **Grade 2** events, monitor liver function tests more frequently until returned to baseline values (consider weekly).
 - Treat with IV or oral corticosteroids
- For **Grade 3-4** events, treat with intravenous corticosteroids for 24 to 48 hours.
- When symptoms improve to Grade 1 or less, a steroid taper should be started and continued over no less than 4 weeks.

- **Renal Failure or Nephritis:**

- For **Grade 2** events, treat with corticosteroids.
- For **Grade 3-4** events, treat with systemic corticosteroids.
- When symptoms improve to Grade 1 or less, steroid taper should be started and continued over no less than 4 weeks.

- **Management of Infusion Reactions:** Signs and symptoms usually develop during or shortly after drug infusion and generally resolve completely within 24 hours of completion of infusion.

Table 5 below shows treatment guidelines for subjects who experience an infusion reaction associated with administration of pembrolizumab (MK-3475).

Table 5 Infusion Reaction Treatment Guidelines

NCI CTCAE Grade	Treatment	Premedication at subsequent dosing
Grade 1 Mild reaction; infusion interruption not indicated; intervention not indicated	Increase monitoring of vital signs as medically indicated until the subject is deemed medically stable in the opinion of the investigator.	None
Grade 2 Requires infusion interruption but responds promptly to symptomatic treatment (eg, antihistamines, NSAIDS, narcotics, IV fluids); prophylactic medications indicated for ≤24 hrs	
Stop Infusion and monitor symptoms. Additional appropriate medical therapy may include but is not limited to:
 
 IV fluids Antihistamines NSAIDS Acetaminophen Narcotics 
Increase monitoring of vital signs as medically indicated until the subject is deemed medically stable in the opinion of the investigator.
 
If symptoms resolve within one hour of stopping drug infusion, the infusion may be restarted at 50% of the original infusion rate (eg, from 100 mL/hr to 50 mL/hr). Otherwise dosing will be held until symptoms resolve and the subject should be premedicated for the next scheduled dose.
 
Subjects who develop Grade 2 toxicity despite adequate premedication should be permanently discontinued from further trial treatment administration.
	
Subject may be premedicated 1.5h (\pm 30 minutes) prior to infusion of pembrolizumab (MK-3475) with:
 
Diphenhydramine 50 mg po (or equivalent dose of antihistamine).
 
Acetaminophen 500-1000 mg po (or equivalent dose of antipyretic).

Grades 3 or 4 Grade 3: Prolonged (ie, not rapidly responsive to symptomatic medication and/or brief interruption of infusion); recurrence of symptoms following initial improvement; hospitalization indicated for other clinical sequelae (eg, renal impairment, pulmonary infiltrates)	
Stop Infusion. Additional appropriate medical therapy may include but is not limited to:
 
 IV fluids Antihistamines NSAIDS Acetaminophen Narcotics Oxygen Pressors Corticosteroids 	No subsequent dosing

NCI CTCAE Grade	Treatment	Premedication at subsequent dosing
Grade 4: Life-threatening; pressor or ventilatory support indicated	
Epinephrine
 
Increase monitoring of vital signs as medically indicated until the subject is deemed medically stable in the opinion of the investigator.
 
Hospitalization may be indicated.
 
Subject is permanently discontinued from further trial treatment administration.
	

Appropriate resuscitation equipment should be available in the room and a physician readily available during the period of drug administration.

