5.2.1.2 Immune-Related Events and Dose Modification (Withhold, Treat, Discontinue)

Dose Modification and Toxicity Management for Immune-related AEs Associated with Pembrolizumab

[figure not shown]
AEs associated with pembrolizumab exposure may represent an immune-related response. These irAEs may occur shortly after the first dose or several months after the last dose of pembrolizumab treatment and may affect more than one body system simultaneously. Therefore, early recognition and initiation of treatment is critical to reduce complications. Based on existing clinical study data, most irAEs were reversible and could be managed with interruptions of pembrolizumab, administration of corticosteroids and/or other supportive care. For suspected irAEs, ensure adequate evaluation to confirm etiology or exclude other causes. Additional procedures or tests such as bronchoscopy, endoscopy, skin biopsy may be included as part of the evaluation. Based on the severity of irAEs, withhold or permanently discontinue pembrolizumab and administer corticosteroids.

Hematological Toxicity Management Guidelines for Pembrolizumab are provided in [Table 3](#). Dose Modification and Toxicity Management Guidelines for irAEs associated with pembrolizumab monotherapy, coformulations, or IO combinations are provided in [Table 4](#).

[figure not shown]
CCI

Toxicity	Grade	Hold Treatment (Y/N)	Timing for restarting treatment	Treatment Discontinuation (after consultation with Sponsor)
CCI				N/A
	4	Yes	Toxicity resolves to Grade 0-1 or baseline	Toxicity does not resolve within 12 weeks of last infusion Permanent discontinuation should be considered for any life-threatening event

[figure not shown]
CCI

CCI

CCI

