7.2.4 Evaluating Adverse Events

An investigator who is a qualified physician will evaluate all adverse events according to the NCI Common Terminology for Adverse Events (CTCAE), version 4.0. Any adverse event which changes CTCAE grade over the course of a given episode will have each change of grade recorded on the adverse event case report forms/worksheets.

All adverse events regardless of CTCAE grade must also be evaluated for seriousness.

Table 10 Evaluating Adverse Events

An investigator who is a qualified physician, will evaluate all adverse events as to:

V4.0 CTCAE Grading	Grade 1	Mild; asymptomatic or mild symptoms; clinical or diagnostic observations only; intervention not indicated.
	Grade 2	Moderate; minimal, local or noninvasive intervention indicated; limiting age-appropriate instrumental ADL.
	Grade 3	Severe or medically significant but not immediately life-threatening; hospitalization or prolongation of hospitalization indicated; disabling; limiting self-care ADL.
	Grade 4	Life threatening consequences; urgent intervention indicated.
	Grade 5	Death related to AE
Seriousness	A serious adverse event is any adverse event occurring at any dose or during any use of Sponsor's product that:	
	† Results in death; or	
	† Is life threatening; or places the subject, in the view of the investigator, at immediate risk of death from the event as it occurred (Note: This does not include an adverse event that, had it occurred in a more severe form, might have caused death.); or	
	† Results in a persistent or significant disability/incapacity (substantial disruption of one's ability to conduct normal life functions); or	
	† Results in or prolongs an existing inpatient hospitalization (hospitalization is defined as an inpatient admission, regardless of length of stay, even if the hospitalization is a precautionary measure for continued observation. (Note: Hospitalization for an elective procedure to treat a pre-existing condition that has not worsened is not a serious adverse event. A pre-existing condition is a clinical condition that is diagnosed prior to the use of an MSD product and is documented in the patient's medical history.); or	
	† Is a congenital anomaly/birth defect (in offspring of subject taking the product regardless of time to diagnosis); or	
	Is a cancer (although not serious per ICH definition, is reportable to the Sponsor within 24 hours to meet certain local requirements); or	

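### Section 5.6.1 suggests a longer wait before steroids for Grade 3 or 4 diarrhea/colitis (more than 1 week) than for Grade 2 (more than 3 days)

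*Combined protocol and SAP*

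**What the plan says.** Section 5.6.1 lists suggested measures, by disorder and grade, for adverse events of possible immune origin that the investigator attributes to pembrolizumab. Two consecutive bullets deal with steroids for diarrhea/colitis:

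- Grade 2: diarrhea/colitis "that persists greater than 3 days, administer oral corticosteroids".
- Grade 3 or 4: diarrhea/colitis "that persists > 1 week, treat with intravenous steroids followed by high dose oral steroids".

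The same section asks sites to watch for enterocolitis and bowel perforation, to replace fluids, and to consider gastrointestinal consultation and endoscopy from Grade 2 upward.

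Section 5.2.1.2 gives the general rule for immune-related events. It states that "early recognition and initiation of treatment is critical to reduce complications", and then: "Based on the severity of irAEs, withhold or permanently discontinue pembrolizumab and administer corticosteroids". The readable text there sets no waiting period. That section also points to Table 4 for detailed toxicity management, but Table 4 is redacted in the public copy.

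**The concern.** Within one disorder, a more severe event would be expected to reach a steroid trigger no later than a milder one. Here the order is reversed. Read literally, a subject with Grade 2 diarrhea on day 5 meets the steroid condition and a subject with Grade 4 diarrhea on day 5 does not. The section gives no reason for this.

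What is at stake is patient safety and a consistent instruction to sites. The event is one for which the section itself warns of perforation. Section 7.1.2.1 sends sites to 5.6.1 for the management of adverse events of potential immune origin, and Section 5.8 cites it among the places that describe unacceptable adverse experiences, so the bullet is text that sites are told to use. Nothing in the efficacy analysis depends on it, and no effect on the safety summaries has been shown.

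**Working it through.** No statistical figure is involved. The check sets the texts side by side.

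**Step 1: the two triggers.** Grade 2: more than 3 days. Grade 3 or 4: more than 1 week, that is, more than 7 days. Gap: 7 − 3 = 4 days, with the higher grades waiting longer.

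**Step 2: the other steroid items in 5.6.1.**

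| Disorder | Grade 2 | Grade 3-4 | Wait at Grade 3-4? |
|---|---|---|---|
| Pneumonitis | systemic steroids, no wait | "immediately treat with intravenous steroids" | No |
| Diarrhea/colitis | oral steroids after more than 3 days | IV, then high-dose oral, after more than 1 week | **Yes** |
| Hypophysitis | steroids, no wait | "treat with an initial dose of IV corticosteroids followed by oral corticosteroids" | No |
| Hyperthyroidism | beta-blocker, no steroid | IV, then oral | No |
| Hepatic | IV or oral steroids, no wait | "treat with intravenous corticosteroids for 24 to 48 hours" | No |
| Renal failure/nephritis | steroids, no wait | systemic steroids | No |

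The hepatic 24 to 48 hours is a duration of treatment, not a delay before it. Type 1 diabetes/hyperglycemia is not counted because its treatment is insulin. Infusion reactions are not counted because steroids are only one option among several. One of 6 Grade 3-4 steroid items has a waiting period; the other 5 have none. Diarrhea/colitis is also the only disorder in the list where the higher grade waits longer than the lower.

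**Step 3: the general rule.** Section 5.2.1.2 makes corticosteroids depend on severity and stresses early treatment. A condition that delays them more as severity rises is at odds with both.

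**Step 4: the grade definition.** Table 10 in Section 7.2.4 describes Grade 4 as: "Life threatening consequences; urgent intervention indicated". This is a grading definition, not a steroid instruction, and it covers Grade 4 only. It supports the point without proving it.

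**Step 5: how many subjects.** Section 4.3 gives Grade 3/4 treatment-related diarrhea as 1% of 210 treated subjects: 0.01 × 210 = 2.1, about 2 subjects (2/210 = 0.95%). The document does not say whether these events were colitis or how long they lasted.

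**The case against.** The strongest reply is that the governing rule may be elsewhere. Table 4 covers toxicity management as well as dosing, and the document history shows that two 2021 amendments were issued to update those guidelines. If Table 4 already calls for prompt steroids in Grade 3-4 colitis, the bullet in 5.6.1 is a leftover line. This cannot be settled from the public copy. It limits what can be claimed about actual delay, but does not make the bullet right: if Table 4 says something earlier, sites hold two different rules.

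Second, 5.6.1 is advisory. It leaves care to the investigator's judgement, does not forbid earlier steroids, and 5.2.1.2 allows them. That stands, and it reduces the practical effect.

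Third, diarrhea/colitis differs from its neighbours at Grade 2 as well. It is the only Grade 2 steroid item with a persistence condition, perhaps because infection must be excluded first. This weakens the comparison with other disorders. It does not explain why that work-up should take longer in Grade 3 or 4 than in Grade 2.

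Fourth, the 4 days are a gap between triggers, not an observed delay. An event that stays at Grade 2 for more than 3 days and then worsens has already met the oral-steroid trigger, so the gap applies mainly to events that start at, or quickly reach, Grade 3 or 4. That is correct.

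Fifth, few subjects can still be affected. The 210 treated subjects were already reported in Section 4.3, first-course treatment is capped at about 24 months, and the latest amendments date from December 2022. What remains is chiefly second-course treatment of up to 17 cycles (Section 7.1.5.2.2), plus late immune events, which 5.2.1.2 says may appear months after the last dose. This bears on urgency, not on whether the line is correct.

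**Conclusion.** The concern holds. As written, 5.6.1 suggests starting steroids later for Grade 3 or 4 diarrhea/colitis than for Grade 2, with a 4-day gap between triggers. The Grade 3-4 condition departs from the other five Grade 3-4 steroid items in the section and from the severity-based rule in 5.2.1.2. None of the objections supplies a reading in which the order makes sense.

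Confidence is high on the wording. No confidence is claimed that any subject was treated late, because the text is advisory, Table 4 cannot be read, and Grade 3/4 related diarrhea was reported in only about 2 of 210 subjects. It should be corrected as a point of safety guidance; it does not bear on the trial's statistical conclusions.

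**What to change.** Delete the one-week persistence condition from the Grade 3 or 4 diarrhea/colitis bullet in 5.6.1, so that it reads like the other Grade 3-4 items, with no waiting period. Then compare the revised bullet with the unredacted Table 4 and make the two agree.

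A weaker alternative is to set the Grade 3 or 4 trigger no later than the Grade 2 trigger of 3 days. That removes the inversion, but it only borrows the Grade 2 figure, and nothing in the document supports 3 days as the right wait for severe events.

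The cost is one line of wording and one cross-check. Design, sample size and analysis do not change.
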